9. DATA COLLECTION AND MANAGEMENT

9.1 Data Collection Tools

- **Physical function tests:** 30-second chair stand test, TUG, SPPB
- **Cognitive tests:** Stroop Color-Word Test, Trail Making Test
- **Questionnaires:** FES, IPAQ, Acceptability Questionnaire

- **Process monitoring:** Exercise log, Borg CR-10 scale, video 抽查

9.2 Data Management

- Electronic data capture system (e.g., REDCap)
- Double data entry with cross-verification
- Data stored on encrypted servers

10. STATISTICAL ANALYSIS

10.1 Analysis Populations

Population	Definition	Purpose
ITT (Intention-to-Treat)	All randomized participants, analyzed according to original group assignment	Primary analysis
PP (Per-Protocol)	Participants with adherence $\geq 80\%$	Sensitivity analysis
Safety Population	Participants who received at least one intervention session	Adverse event analysis

10.2 Statistical Methods

Analysis Purpose	Statistical Method
Baseline characteristics comparison	One-way ANOVA or chi-square test
Within-group changes	Paired t-test or Wilcoxon signed-rank test
Between-group differences	4 × 3 mixed ANOVA, post-hoc Tukey HSD
Trend analysis	Polynomial contrast (linear, quadratic)
Effect sizes	Cohen's d (within-group), η^2 (between-group)

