3. STUDY DESIGN

Design Overview

- **Design:** Four-arm parallel-group randomized controlled pilot trial

- **Allocation Ratio:** 1:1:1:1
- **Masking:** Assessor-blind (outcome assessors unaware of group assignment)
- **Intervention Period:** 8 weeks
- **Assessment Time Points:** Baseline (Week 0), Mid-intervention (Week 4), Post-intervention (Week 8)

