4.3 Sample Size

As a pilot trial, formal power calculation is not performed. Fifteen participants per group (total N=60) will be recruited. Anticipating a 20-25% attrition rate, approximately 45 participants (11-12 per group) are expected to complete the 8-week intervention.

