6.2 Secondary Outcome Measures

Outcome	Measure	Time Points
Comprehensive Physical Function	Short Physical Performance Battery (SPPB). Composite score (0-12) based on standing balance (0-4), 4-meter gait speed (0-4), and 5-repetition chair stand time (0-4). Higher score indicates better function.	Baseline, Week 4, Week 8
Executive Function - Inhibition Control	Stroop Color-Word Test (SCW). Three parts: Word, Color, and Color-Word. Interference effect (SCW score ÷ Color score) is calculated. Lower values indicate better inhibition control.	Baseline, Week 4, Week 8
Executive Function - Cognitive Flexibility	Trail Making Test (TMT). TMT-A (numbers 1-25) and TMT-B (alternating numbers and letters). Difference (TMT-B minus TMT-A) is calculated. Smaller differences indicate better cognitive flexibility.	Baseline, Week 4, Week 8
Falls Efficacy	Modified Falls Efficacy Scale (FES). 16-item questionnaire (0-10 per item, total 0-160). Higher scores indicate better falls efficacy.	Baseline, Week 8

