8. RANDOMIZATION AND BLINDING

8.1 Randomization

- **Method:** Online random number generator (Sealed Envelope)
- **Allocation Ratio:** 1:1:1:1
- **Stratification Factors:** Sex, baseline SPPB score (3-6 vs. 7-10)

- **8.2 Blinding**

Role	Blinded?
Participants	No
Intervention Providers	Yes
Outcome Assessors	Yes
Data Analysts	Yes

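### The 4 × 3 mixed ANOVA makes baseline an outcome level and names no test of interest: a group main effect would be diluted, and the valid interaction test usually gives up efficiency against baseline adjustment

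*Protocol*

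**What the plan says.** Section 3 describes a "Four-arm parallel-group randomized controlled pilot trial" with assessments at "Baseline (Week 0), Mid-intervention (Week 4), Post-intervention (Week 8". For between-group differences, section 10.2 lists "4 × 3 mixed ANOVA, post-hoc Tukey HSD", and the abstract repeats the 4 × 3 mixed ANOVA as the way arms will be compared. No covariate is named, and neither the main effect nor the interaction is singled out. The same table lists linear and quadratic polynomial contrasts, without saying whether they run across arms or across visits, and gives eta-squared as the between-group effect size. The abstract says effect sizes are to inform a later definitive trial.

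Section 8.1 stratifies randomization by "Sex, baseline SPPB score (3-6 vs. 7-10"), so both factors are known at baseline. Section 6.2 describes the falls efficacy scale as a "16-item questionnaire (0-10 per item, total 0-160). Higher scores indicate better falls efficacy"; its time-point column lists only Baseline and Week 8. Sections 4.3 and 10.4 make no power claim. Section 10.1 bases the primary analysis on "All randomized participants, analyzed according to original group assignment", and section 10.3 provides multiple imputation.

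**The concern.** With baseline as one of three repeated levels, the group main effect is not the treatment effect at the end of the intervention. It is the average of one visit that cannot differ in expectation and two visits that can. Tukey comparisons of the group marginal means, and an eta-squared for group, inherit that averaging. The method line does not exclude this reading.

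The stake is estimation more than a significance test. Section 10.4 justifies 60 participants by effect-size estimation, and the abstract sends those estimates forward to a definitive trial. An eta-squared that averages in baseline would misstate the signal on which that trial is sized. Separately, the baseline value is collected but not used as a covariate, which costs precision when there are only 15 participants per arm.

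**Working it through.** **The plan's own figure.** Section 4.3 recruits 60 and states "Anticipating a 20-25% attrition rate, approximately 45 participants (11-12 per group) are expected to complete the 8-week intervention". At 25% attrition, 60 × 0.75 = 45, or 11.25 per arm; at 20%, 60 × 0.80 = 48, or 12 per arm. The figure reproduces. The Protocol states no power, effect size, SD or correlation, so those below are assumptions.

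**Dilution (needs no SD or correlation).** Write the arm difference at Weeks 0, 4 and 8 as multiples of the Week 8 difference. The main effect estimates their mean.
- Linear growth: (0 + 0.5 + 1)/3 = 1/2
- Complete by Week 4: (0 + 1 + 1)/3 = 2/3
- Week 8 only: (0 + 0 + 1)/3 = 1/3

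The squared signal that feeds eta-squared falls to 1/4, 4/9 and 1/9 of its Week 8 value.

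**Efficiency (assumed values).** Take SD 1, two-sided alpha 0.05, Week 8 arm means evenly spaced over 0.8 SD, and equal correlation r between visits (compound symmetry). The arm means are 0, 0.267, 0.533 and 0.8, so the sum of squared deviations is S = 2 × (0.4² + 0.133²) = 0.356. With n = 15 per arm, nS = 5.33. Let t be the visit multipliers above and m their mean. The noncentralities are:
- main effect: nS × 3m²/(1 + 2r), on 3 and N − 4 df
- interaction: nS × Σ(t − m)²/(1 − r), on (4 − 1)(3 − 1) = 6 and 2(N − 4) df
- Week 8 ANCOVA: nS/(1 − r²), on 3 and N − 5 df

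Linear growth, r = 0.7, N = 60:
- main effect: 5.33 × 0.75/2.4 = 1.67, power 16%
- interaction: 5.33 × 0.5/0.3 = 8.89, power 56%
- Week 8 ANCOVA: 5.33/0.51 = 10.46, power 75%

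Other settings, interaction against Week 8 ANCOVA:

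| Pattern | r | N | Interaction | Week 8 ANCOVA |
|---|---|---|---|---|
| Linear | 0.5 | 60 | 34% | 56% |
| Linear | 0.7 | 45 | 41% | 60% |
| Equal at Weeks 4 and 8 | 0.7 | 60 | 70% | 75% |
| Equal at Weeks 4 and 8 | 0.8 | 60 | 89% | 89% |

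In the last row the noncentralities are 5.33 × 0.667/0.2 = 17.78 and 5.33/0.36 = 14.81; the interaction's larger value is offset by its 6 df. Simulation (4,000 runs per setting) agreed with these calculations within about 2 points, with type I error near 5% for every test.

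**One-degree-of-freedom contrast.** If the polynomial contrast in section 10.2 runs across arms, evenly spaced means put all of S into the linear term. At r = 0.7 and N = 60, the contrast on Week 0 to Week 8 change has noncentrality 5.33/0.6 = 8.89 and power 83%. The same contrast in ANCOVA has 10.46 and 89%.

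**Why adjustment cannot lose signal.** Under compound symmetry, the covariance matrix of the two changes equals that of Weeks 4 and 8 given baseline, plus (1 − r)² times a matrix of ones. A baseline-adjusted joint test of both visits therefore never has a smaller noncentrality than the interaction.

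**The case against.** The strongest reply is that the interaction is the natural test of differential change in such a design. It is valid and contains no dilution, and the Protocol never names the main effect as primary. That stands: the 16% figure describes one possible reading and should not be quoted as this trial's power. The reply does not remove the ambiguity, because the method line leaves both tests and the source of eta-squared open.

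Second, the efficiency gain is not universal. It rests on assumed effects and correlations, and the two tests tie in the last row of the table. Under first-order autoregressive correlation with an equal effect at both visits, simulation has the interaction ahead of Week 8 ANCOVA: 60% against 57% at r = 0.7, and 87% against 77% at r = 0.85. An effect present only at Week 4 would be missed by a Week 8 contrast. This also stands, and it is why the remedy models both visits; naming Week 8 is a choice of target. Like for like on a linear contrast across arms, the gain is only 83% to 89%.

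Third, this is a pilot with no power claim. That lowers the weight of the power comparison but not of the dilution, since effect-size estimation is a declared aim.

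Two stronger readings are tempting and are not supported. A reader might infer that leaving out sex and SPPB stratum causes the dilution or the loss in the interaction. It causes neither: both come from baseline being an outcome level, and a stratum effect constant over time cancels from the within-participant interaction. The omission only enlarges the error term of the main effect. A reader might also infer that participants missing a visit are dropped. Section 10.3 specifies multiple imputation and section 10.1 analyses everyone randomized, so the N = 45 row is only an illustration with completers.

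**Conclusion.** The point holds as a recommended change, not as an invalid analysis. The dilution to 1/2, 2/3 or 1/3 of the Week 8 effect follows from the design alone, and applies if the group main effect, its Tukey comparisons or its eta-squared are reported as the between-arm result. The interaction is valid and undiluted but generally less efficient than a baseline-adjusted analysis. Its shortfall against Week 8 ANCOVA is about 19 points (56% against 75%) in the central assumed case, 5 points with an equal effect at both visits and r = 0.7, and nil at r = 0.8; under autoregressive correlation it can reverse. For a linear contrast across arms the gain is about 6 points. These power figures rest on an assumed 0.8 SD range and, except for the reversal, on compound symmetry. The falls efficacy mismatch needs no assumption: two visits cannot supply three time levels.

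**What to change.** In the abstract and section 10.2, replace the mixed ANOVA by a linear mixed model with Week 4 and Week 8 values as outcomes, terms for arm, visit and arm-by-visit, and adjustment for the baseline value of the outcome, sex and baseline SPPB stratum. Name the adjusted Week 8 arm contrasts with 95% confidence intervals as the primary between-group result, and take the between-group effect sizes from that model. For falls efficacy, use ANCOVA at Week 8 with the corresponding baseline covariates. The multiple imputation in section 10.3 can stay.

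The cost is revised wording, slightly more analysis code and a few degrees of freedom for the covariates. Every variable needed is already collected.

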1. ABSTRACT

Background: Exercise snacks have emerged as a promising strategy to improve physical function in older adults. However, the optimal fragmentation pattern (i.e., how to distribute a fixed daily volume of exercise across the day) remains unknown. Furthermore, the effects of resistance-based exercise snacks on cognitive function in pre-frail older adults have not been investigated.

Objective: To compare the effects of four different fragmentation patterns of a three-exercise resistance snack (sit-to-stand, squat, and heel raise) on lower limb strength, dynamic balance, and executive cognitive function in community-dwelling pre-frail older adults.

Design: Four-arm parallel-group randomized controlled pilot trial.

Participants: 60 community-dwelling pre-frail older adults (Fried Frailty Phenotype score 1-2, aged ≥ 65 years).

Interventions: All groups perform a fixed total daily volume of 15 repetitions per exercise (sit-to-stand, squat, and heel raise), resulting in 45 total repetitions per day. The only difference between groups is the fragmentation pattern:

- G1 (highly fragmented): 1 repetition of each exercise per bout, 15 bouts/day (~30 seconds per bout)
- G2 (moderately fragmented): 3 repetitions of each exercise per bout, 5 bouts/day (~90 seconds per bout)
- G3 (lowly fragmented): 5 repetitions of each exercise per bout, 3 bouts/day

(~2.5 minutes per bout)

- G4 (consecutive control): 15 repetitions of each exercise per bout, 1 bout/day (~7.5 minutes per bout)

The intervention period is 8 weeks.

Outcome Measures: Primary outcomes include lower limb strength (30-second chair stand test) and dynamic balance (Timed Up and Go test). Secondary outcomes include comprehensive physical function (Short Physical Performance Battery), executive function (Stroop Color-Word Test and Trail Making Test), and falls efficacy (modified Falls Efficacy Scale). Feasibility outcomes include adherence, acceptability, and adverse events.

Data Analysis: A 4×3 mixed ANOVA will be used to compare group differences. Effect sizes (Cohen's d , η^2) will be estimated to inform a future definitive randomized controlled trial.

Expected Results: This pilot trial will provide preliminary evidence on the dose-response relationship between exercise snack fragmentation patterns and both physical and cognitive outcomes in pre-frail older adults.

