2.4 Study Objectives

This study aims to:

1. Compare the effects of four different fragmentation patterns on lower limb function and executive cognitive function in pre-frail older adults
2. Explore the dose-response relationship between fragmentation pattern and intervention effects
3. Determine whether 15 repetitions per day is above, at, or below the minimal effective dose threshold for resistance-based exercise snacks

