6. OUTCOME MEASURES

6.1 Primary Outcome Measures

Outcome	Measure	Time Points
Lower Limb Muscle Strength	30-Second Chair Stand Test (30-CST). Number of complete sit-to-stand repetitions within 30 seconds. Higher score indicates better strength.	Baseline, Week 4, Week 8
Dynamic Balance and Mobility	Timed Up and Go (TUG) test. Time (seconds) to stand from a chair, walk 3 meters, turn, walk back, and sit down. Shorter time indicates better balance and mobility.	Baseline, Week 4, Week 8

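### The 4 × 3 mixed ANOVA makes baseline an outcome level and names no term or visit for comparing arms; if the group main effect is meant, Week 8 arm differences shrink by one third to two thirds

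*Protocol*

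**What the plan says.** In the protocol, the methods table of section 10.2 gives "4 × 3 mixed ANOVA, post-hoc Tukey HSD" for differences between arms. The abstract gives the same model and its purpose: "A 4×3 mixed ANOVA will be used to compare group differences".

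Section 3 lists the assessments as "Baseline (Week 0), Mid-intervention (Week 4), Post-intervention (Week 8". Section 6.1 schedules both primary outcomes, the 30-second chair stand and the Timed Up and Go, at "Baseline, Week 4, Week 8". With four arms, the 3 in the layout can only be these visits, baseline included. Section 8.1 stratifies on baseline SPPB, which places the baseline assessment before allocation.

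Two further rows of 10.2 depend on the same model. The trend analysis is "Polynomial contrast (linear, quadratic" and the effect sizes are "Cohen's d (within-group), η^2 (between-group". Neither row gives the factor, the model term or the visit. The second objective in section 2.4 is "Explore the dose-response relationship between fragmentation pattern and intervention effects".

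Section 10.2 does not mention a group × time interaction, a change score, a Week 8 contrast or a baseline covariate.

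**The concern.** Arms that have been randomized but not yet treated have no expected difference at baseline. A mixed ANOVA with baseline as a level therefore has a group main effect that averages one null visit with two informative ones. Tukey comparisons of arms, and polynomial contrasts across arms, inherit that average if they are run on the arm marginal means. So does an η² taken from the group effect.

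The abstract says that effect sizes from this pilot are to inform a definitive trial. A diluted arm difference would make the fragmentation patterns look more alike than they are, and that understatement would carry into the next design. The baseline value, which every outcome has, would also not be used to reduce error variance.

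**Working it through.** **Inputs from the protocol.** Four arms and three visits (sections 3 and 6.1). For sample size, "Fifteen participants per group (total N=60) will be recruited" (section 4.3), with 20-25% attrition.

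**The plan's own figures.** 15 × 4 = 60. 60 × 0.75 = 45 and 60 × 0.80 = 48, or 11.25 to 12 per arm, which agrees with the stated 45 or so completers. No power, effect size, SD, visit correlation or alpha is stated, so there is no power figure to reproduce.

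**Assumptions.** Two-sided 5%; SD 1 at each visit; equal correlation ρ between visits; Week 8 effects falling linearly from G1 to G4. Let f be the Week 4 effect divided by the Week 8 effect.

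**Step 1: what the main effect estimates.** With a true Week 8 difference Δ, the difference in three-visit means is Δ × (0 + f + 1)/3.

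| f | Share of Δ kept | Share lost |
|---|---|---|
| 1 | 0.667 | one third |
| 0.75 | 0.583 | 42% |
| 0.5 | 0.500 | one half |
| 0.25 | 0.417 | 58% |
| 0 | 0.333 | two thirds |

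The protocol does not give f. In section 5.4 the progression phase is Weeks 6-8, after the Week 4 visit, so values well below 1 cannot be ruled out.

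**Step 2: precision for one pair of arms.** Averaging also changes the variance, so power need not fall in proportion.

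- SD of the three-visit mean: √((1 + 2ρ)/3), which is √0.80 = 0.894 at ρ = 0.7.
- SD of baseline-adjusted Week 8: √(1 − ρ²) = √0.51 = 0.714.
- SD of Week 8 minus baseline, the contrast inside the interaction: √(2(1 − ρ)) = √0.60 = 0.775.

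For Δ = 1 SD and 15 per arm, without multiplicity adjustment, power is:

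- main effect: 0.33 (f = 0.5) or 0.53 (f = 1)
- Week 8 minus baseline: 0.94
- baseline-adjusted Week 8: 0.97

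At 11.25 per arm the same figures are 0.26 or 0.42, 0.87 and 0.91.

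**Step 3: four-arm tests by simulation.** 4,000 trials per setting, 15 per arm, Week 8 effects 1, 2/3, 1/3 and 0 SD.

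| f | ρ | Main effect (3 df) | Interaction (6 df) | Week 8 ANCOVA (3 df) |
|---|---|---|---|---|
| 0.5 | 0.5 | 0.27 | 0.54 | 0.78 |
| 0.5 | 0.7 | 0.23 | 0.80 | 0.92 |
| 0.5 | 0.9 | 0.20 | 1.00 | 1.00 |
| 1 | 0.5 | 0.46 | 0.67 | 0.77 |
| 1 | 0.7 | 0.39 | 0.91 | 0.92 |
| 1 | 0.9 | 0.34 | 1.00 | 1.00 |

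The mean estimate of the G1-G4 difference (true value 1.00) was about 0.50 (f = 0.5) or 0.67 (f = 1) from the marginal means. It was 1.00-1.01 from both the Week 8 minus baseline contrast and ANCOVA. The linear arm contrast (true value 3.33) was 1.66-1.68 or 2.22-2.23 from the marginal means, and 3.33-3.36 from ANCOVA.

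**Step 4: a smaller effect.** With a 0.8 SD G1-G4 difference, ρ = 0.6-0.8, f = 0.5 and 15 per arm, Step 1 gives 0.8 × 0.5 = 0.40 SD. Simulation gave 0.40 SD from the marginal means and 0.80-0.81 SD from Week 8 ANCOVA. Simulated power was:

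- omnibus test: main effect 15-17%, interaction about 44-77%, ANCOVA 64-89%
- Tukey G1 against G4: 9% on marginal means, 54-84% on adjusted Week 8 means
- linear trend across arms: 25-27% against 80-97%

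**The case against.** The strongest reply is that the diluted quantity is only one output of the model. A 4 × 3 mixed ANOVA also contains the group × time interaction. Its Week 8 minus baseline contrast was undiluted in every setting above and came close to ANCOVA in pairwise power. The protocol does not say that the group main effect is the test, that Tukey runs on marginal means, or that the polynomial runs over arm rather than time. These details may be in a statistical analysis plan that is not at hand.

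That reply stands in part. A reader might infer that every planned arm comparison is biased toward no difference. The documents do not support this, because they leave the term open.

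It does not remove the point. The protocol fixes the model and its three levels, and leaves baseline out as a covariate. Its wording, in the abstract and in the 10.2 row labels, speaks of group differences and never of an interaction, and a dose-response objective points to contrasts across arms. Reading the model as the interaction still leaves an omnibus test that does not order the four patterns.

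Two further objections are fair. The size of the loss rests on an assumed Week 4 effect. And no power is promised, so low power for a Tukey pair breaks no commitment.

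**Conclusion.** The point holds in conditional form. As written, 10.2 and the abstract make baseline an outcome level and leave open which term and visit give the arm comparison, so the same data could give two quite different answers.

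- **Group main effect.** The expected Week 8 difference is cut by one third to two thirds, depending on f. The marginal-mean Tukey pairs, arm trends and any η² taken from that effect are diluted with it. This is algebra and needs only a null baseline difference.
- **Interaction.** Nothing is diluted. Omnibus power is usually below that of baseline-adjusted Week 8, and about equal when visit correlation is high and the full effect is present by Week 4.

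The power figures rest on assumed effect sizes, correlations and a linear gradient. A reader might go further and call the analysis a failure. That does not follow for a pilot with no power calculation and with an undiluted contrast available in the same model. This is a should-fix: the main harm is to the effect sizes passed on to the definitive trial.

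**What to change.** In section 10.2 and the abstract, replace the 4 × 3 mixed ANOVA with a repeated-measures model of the post-baseline values. Week 4 and Week 8 are the outcomes; arm, visit and arm × visit are factors; the baseline value of the same measure is a covariate. State that the Tukey comparisons, the linear and quadratic contrasts across arms and the between-group effect sizes all come from the adjusted Week 8 means. Report Week 4 as supportive.

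Falls efficacy is measured only at Baseline and Week 8 (section 6.2), so neither the 4 × 3 layout nor the two-visit model fits it. Use a Week 8 ANCOVA on baseline for that outcome.

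The cost is protocol wording, modest changes to code and one or two degrees of freedom. No visit, measurement or participant is added. In every setting run, the baseline-adjusted Week 8 comparison was as good as or better than either ANOVA term. The change should be made before any outcome is analysed by arm, so that the choice of term cannot depend on the results.

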5. INTERVENTION

5.1 Four-Group Design Overview

All groups perform a fixed total daily volume of 15 repetitions per exercise (sit-to-stand, squat, and heel raise), resulting in 45 total repetitions per day. The only difference between groups is the fragmentation pattern.

Group	Repetitions per Bout (per exercise)	Bouts per Day	Duration per Bout	Fragmentation Level
G1 (Highly Fragmented)	1	15	~30 seconds	Highest
G2 (Moderately Fragmented)	3	5	~90 seconds	Moderate
G3 (Lowly Fragmented)	5	3	~2.5 minutes	Lower
G4 (Consecutive Control)	15	1	~7.5 minutes	None

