5.3 Triggering Strategies

Group	Trigger Type	Specific Instructions
G1	Event-based	Perform one bout after each bathroom visit and after each time drinking water
G2	Fixed time points	Perform bouts at approximately 9:00, 12:00, 15:00, 18:00, and 21:00
G3	Fixed time points	Perform bouts at morning (9:00), noon (14:00), and evening (19:00)
G4	Fixed time	Perform the single daily bout at a consistent time (e.g., 10:00 AM)

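### Section 5.1 says that only fragmentation differs between the arms, but G1 alone is cued by events, so the four-arm trend in section 10.2 cannot be attributed to fragmentation alone

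*Protocol*

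**What the plan says.** Objective 2 in section 2.4 is to "Explore the dose-response relationship between fragmentation pattern and intervention effects". Of the methods in section 10.2, only the trend analysis, "Polynomial contrast (linear, quadratic", fits that objective. The table does not name the factor or the scores.

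Section 5.1 says of the four arms that "The only difference between groups is the fragmentation pattern", and section 1 says the same. The schedules in section 1 are:

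- G1: "1 repetition of each exercise per bout, 15 bouts/day"
- G2: "3 repetitions of each exercise per bout, 5 bouts/day"
- G3: "5 repetitions of each exercise per bout, 3 bouts/day"
- G4: "15 repetitions of each exercise per bout, 1 bout/day"

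Section 5.3 labels the G1 trigger event-based: "Perform one bout after each bathroom visit and after each time drinking water". G2 and G3 have listed clock times, and G4 has one consistent time of day.

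Section 5.4 adds further differences. Repetitions per bout rise in G2 and G3 in weeks 3–5, and an optional weighted vest is offered to G3 and G4 in weeks 6–8.

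**The concern.** The trend treats the four arms as steps on one scale of fragmentation, but the arm at the top of that scale also changes the kind of cue. Randomization does not help, because the cue is part of what is assigned. The problem remains even if every G1 participant completes exactly 15 bouts a day, so it is separate from any question about the volume that G1 achieves.

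At stake is what the pilot hands on. Section 1 says that effect sizes will inform a definitive trial and promises preliminary dose-response evidence. If the cue did matter, its effect would be reported as a slope or curvature of fragmentation, and the later trial would start from the wrong shape.

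**Working it through.** **Stated volume.** Repetitions per bout times bouts per day: 1 × 15 = 3 × 5 = 5 × 3 = 15 × 1 = 15 per exercise, and 15 × 3 exercises = 45 per day. This reproduces sections 1 and 5.1, so the schedules as first prescribed do match on volume.

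**Aliasing.** Code the cue as (G1, G2, G3, G4) = (1, 0, 0, 0). A model with an intercept, three arm indicators and the cue has five columns but rank 4, so the cue cannot be separated from G1. Adding the cue to a linear trend model does not rescue G1: the indicator fits the G1 mean exactly, and the slope then comes from G2–G4 alone.

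**Size in the linear trend.** Assume that the contrast runs across arms, that arm sizes are equal (1:1:1:1), that fragmentation has no effect, and that the cue shifts G1 alone by d. With scores x, deviations from their mean z and S = Σz², the fitted slope is z₁d/S. The false G1–G4 difference is z₁(x₁ − x₄)d/S, and the G1 share of the leverage is z₁²/S. The protocol gives no scores, so four choices are shown.

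| Scores (G1, G2, G3, G4) | z₁ | S | G1 leverage | False G1–G4 difference |
|---|---|---|---|---|
| Equal spacing (3, 1, −1, −3) | 3 | 20 | 9/20 = 45% | 3 × 6/20 = 0.90d |
| Bouts per day (15, 5, 3, 1) | 9 | 116 | 81/116 = 70% | 9 × 14/116 = 1.09d |
| Log bouts (2.708, 1.609, 1.099, 0) | 1.354 | 3.797 | 1.833/3.797 = 48% | 1.354 × 2.708/3.797 = 0.97d |
| Repetitions per bout (1, 3, 5, 15) | −5 | 116 | 25/116 = 22% | (−5)(−14)/116 = 0.60d |

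**With the quadratic term added,** least squares gives false G1–G4 differences of 0.90d, 0.99d, 0.97d and 0.87d, in the same order. The share of the cue pattern that the two terms absorb (R² of the cue indicator) is 93.3%, 99.9%, 97.7% and 84.1%. The linear term alone absorbs 60.0%, 93.1%, 64.4% and 28.7%. The equal-spacing case can be checked by hand. The centred indicator has sum of squares 0.75, and the cubic contrast (1, −3, 3, −1) takes 1/20 = 0.05 of it. That leaves 1 − 0.05/0.75 = 93.3%; the linear part is 0.45/0.75 = 60%.

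**Illustration, with an assumed d.** Take d = 0.5 SD, 15 per arm, 56 degrees of freedom, a two-sided 5% test and no fragmentation effect. The noncentrality is dz₁/√(S/15): 1.30 (equal spacing), 1.62 (bouts per day), 1.35 (log bouts) and −0.90 (repetitions per bout). The linear contrast is then significant in 25%, 36%, 26% and 14% of trials, instead of 5%. With d = 0.2 SD the figures are 8%, 10%, 8% and 6%.

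**Precision of a trend over G2–G4.** With equal arm sizes, the slope standard error grows by the square root of the ratio of S for four arms to S for three:

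- per arm step: √(5/2) = 1.6
- bouts per day: √(116/8) = 3.8
- log bouts: √(3.80/1.35) = 1.7
- repetitions per bout: √(116/82.7) = 1.2

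**The case against.** The strongest reply is that no cue effect has been shown. A cue would act mainly through the number of bouts done; with that held at 15, the documents offer no route to strength, balance or executive function. This stands as a limit on what can be claimed. It does not restore the statement in section 5.1, and the design cannot rule such an effect out.

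Second, the trial is an unpowered pilot, Objective 2 is exploratory, the triggers are openly tabulated, and the planned Tukey comparisons already give G2–G3, G2–G4 and G3–G4 free of the cue difference. All true, and this lowers the weight of the point. It does not stop the four-arm trend being read as a fragmentation effect.

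Third, a reader might infer that G1 dominates the trend and that nearly all of any cue effect must appear in it. That holds only for some scores. On repetitions per bout, which section 5.1 tabulates beside bouts per day, G4 carries 81/116 = 70% of the leverage, G1 carries 22%, and the linear figure is 0.60d.

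Fourth, a reader might infer that G2–G4 form a clean scale and should carry the main analysis. Section 5.4 contradicts this: G4 has no planned rise in repetitions per bout, and G2 is not offered the vest. A primary trend over G2–G4 would exchange a cue confound for differences in repetitions and load, at a cost in precision. A quadratic through three means is also saturated, so its fit could not be checked. This objection succeeds against a three-arm primary analysis, but not against a sensitivity analysis.

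**Conclusion.** The point holds in a limited form. The protocol claims a property that its own trigger and loading tables contradict. Cue type is fully aliased with G1, and the four-arm trend estimates the effect of the assigned patterns as packages. A cue shift d in G1 alone would give a false linear G1–G4 difference of 0.60d to 1.09d, depending on the scores.

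This rests on three assumptions: the contrast is applied across arms, arm sizes are equal, and the cue effect is confined to G1. The size of d is unknown, and nothing in the documents shows that it differs from zero. The lack of stated scores is not itself a criticism, since an analysis plan may fix them; it is the reason for a range. No analysis plan could separate cue from fragmentation in this design; it can only label or restrict the contrast.

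**What to change.** 1. Reconcile the sole-difference statement in sections 1 and 5.1 with sections 5.3 and 5.4. Naming cue type alone would leave the statement untrue, because of the section 5.4 differences. Which text should change is for the trial team.
2. If section 5.3 stays as written, keep the four-arm trend in section 10.2, but describe it as the effect of the whole assigned pattern, including cue type, and not of fragmentation alone.
3. Pre-specify a contrast of G1 with G2–G4, labelled as high fragmentation plus event cue.
4. Add the linear trend across G2–G4 as a sensitivity analysis. State that it is free of the cue difference but still subject to the section 5.4 differences.

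The cost is wording, one added contrast and one sensitivity analysis; no trigger, dose or visit changes. The G2–G4 slope is less precise: its standard error is about 1.6 times larger per arm step and about 3.8 times larger on bouts per day. With 11–12 completers expected per arm (section 4.3), it should stay a sensitivity analysis.
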